Statistical Analysis Plan

Study Title: The effects of PF-04995274 on emotional processing in treatment-resistant, medicated, depressed patients (RESTART study).

CT REGISTRATION: NCT03515733. ETHICS REF: 18/SC/0074

Objectives

The primary aim of the study is to investigate the effects of 7 days of PF-04995274 administration (adjunctive to SSRI/SNRI medication) on behavioural measures of non-emotional and emotional cognition, specifically memory performance on an auditory verbal learning task and performance (including accuracy and reaction times) on a facial expression recognition task. The secondary aim of the study is to investigate the effects of 7 days of PF-04995274 administration (adjunctive to SSRI/SNRI medication) on other behavioural measures of non-emotional and emotional cognition.

Brief summary of design

This study uses a double-blind, placebo-controlled, randomised between-groups design. Participants are patients who fulfil criteria for current episode of Major Depressive Disorder (MDD) and are currently taking an SSRI/SNRI and have failed to response clinically. Participants will be randomised to receive 7-9 days treatment with either PF-04995274 (15 mg daily) or a matched placebo. This study includes three visits in total: (a) Screening Visit; (b) First Dose Visit; (c) Research Visit Two. All visits will take place at the Warneford Hospital, Oxford University Department of Psychiatry.

Determination of Sample Size

We will recruit 50 participants to the study (25 on PF-0499574 and 25 on placebo). Participants who withdraw during the study or do not provide complete data-sets will be replaced. Based on data acquired in Harmer et al., (2004) comparing citalopram to placebo, if we aim for 0.9 power and a 0.05 false positive rate, a suggested group sample size is 19 (G*power) to ensure determination of group level differences at this variable if they exist. As 5HT4 agonism is less well studied, and to account for the exclusion of low quality data before analysis, we will aim for 25 individuals with complete datasets per group (total sample size of 50).

Data Cleaning

- Will be performed prior to unblinding
- Outliers will be excluded on a per task basis
- For all behavioural data, excluding the EPS, cut-off thresholds will be determined based on a visual inspection of a histogram plot, examining thresholds for:
 - > Trials with unusually low response times
 - > Trials with unusually high response times

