	List A short delay	Between-subject factor – 2 levels: Treatment group (PF-
	Number of words recalled -	04995274 or placebo)
	List A long delay	Within-subject factor - 2 levels (List A short and long delay
		trials)
	Number of intrusions (words incorrectly recalled) across	Independent samples t-tests
	List A acquisition trials	
	Number of repetitions (words repeated within the same	
	trial) across List A acquisition trials	
	Number of words recalled -	
	List B recall	
	Number of hits and false alarms in the delayed	
	recognition test	
Probabilistic Instrumental	% Accuracy (correct or incorrect symbol choice)	Independent samples t-tests
Learning Task (PILT)	Correct = symbol associated with high probability of	
	winning or low probability of losing	
Reward sensitivity	Proportion of group choosing correct symbol per trial	The proportion will be calculated, and plotted on a learning curve
		to determine where learning plateaus.
Neurobehavioral Systems		
Presentation software		Repeated measures analyses of variance (ANOVAs) - trials where
(https://www.neurobs.com)		learning has plateaued
		Between-subject factor – 2 levels: Treatment group (PF-
		04995274 or placebo)
		 Within-subject factor – 2 levels: Condition (win or loss)
	Learning rate from reinforcement learning model	Repeated measures analyses of variance (ANOVAs)
		Between-subject factor – 2 levels: Treatment group (PF-
		04995274 or placebo)
		Within-subject factor – 2 levels: Condition (win or loss)

	Decision temperature parameters from reinforcement learning model	 Repeated measures analyses of variance (ANOVAs) Between-subject factor – 2 levels: Treatment group (PF-04995274 or placebo) Within-subject factor – 2 levels: Condition (win or loss)
	Amount won Amount lost Total monetary amount earned	Independent samples t-tests
Emotional Categorisation Task (ECAT) Categorisation of emotional words	% Accuracy – words correctly identified as positive or negative	 Mixed model analyses of variance (ANOVAs). Between-subject factor – 2 levels: Treatment group (PF-04995274 or placebo) Within-subject factor – 2 levels: Word valence (positive or negative)
P1vital® Limited Products Emotional Recall Task (EREC)	Reaction time Number of hits (words recalled correctly) Number of false alarms (words recalled incorrectly)	
Recall of emotional words from ECAT P1vital® Limited Products		
Emotional Recognition Task (EMEM)	Number of hits (words recognised correctly) Number of false alarms (words recognised incorrectly)	

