Visual Analogue Scales (VAS)	Total score for each VAS (happy, sad, hostile, alert, anxious, calm)	Pre-ETB, Post-ETB)	
Side effects	Presence of side effect Severity of side effect Belief in relationship to drug	Descriptive report of frequency of side-effects for each group at four time points (baseline, pre-dose, post-dose and all other study days combined).	
		A generalised linear model will be used to analyse side effects, with presence of side-effect as outcome and predictors including treatment group (PF-04995274 or placebo) and time point (baseline, pre-dose, post-dose, day 2/3/4/5/6/7/8/9).	
		For side effects significantly associated with group and time-point, we will investigate severity and belief in relationship to study drug.	

When conducting ANOVAs, the Greenhouse-Geisser procedure will be used to correct the degrees of freedom where assumptions of equality of variance are violated. If there is a significant group x condition interaction found in ANOVAs. Post hoc independent samples t tests will be performed to follow up any significant interactions. We will not use the Bonferroni correction for multiple comparisons for post-hoc tests. When conducting t tests, degrees of freedom will be corrected where the assumption of equal variances between groups is violated (i.e. Levene's Test is significant).

Record of version changes and unblinding

Date	Version	Blinding Status	Comments
28 th October 2022	1.0	Team blinded, barring unblinding for study medics (AdeC, PC and BG) where necessary.	Data collection complete. First version of complete stats plans. Uploaded to clinicaltrials.gov and OSF.

Study Team involved in analysis

AdeC - [name] [name] - DPhil Student, Study Medic

AG - [name] – Post-doctoral Researcher

BG - [name] - Study Medic

CH - [name] - Principal Investigator

MB - [name] - Research Assistant

PC - [name] – Principal Investigator, Study Medic

SM - [name] - Senior Research Fellow

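### Use Welch's t test unconditionally instead of only after a significant Levene's test: a small but nearly free gain in error control when per-task exclusions leave unequal groups

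*SAP*

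**What the plan says.** The paragraph after the SAP's analysis tables sets one rule for all t tests: "degrees of freedom will be corrected where the assumption of equal variances between groups is violated (i.e. Levene's Test is significant"). It states neither a significance level for Levene's test nor whether deviations are taken from the mean or the median. It does not name the corrected test. I read it as the usual unequal-variance (Welch) test.

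The Behavioural Analysis table assigns "Independent samples t-tests" to AVLT intrusions, repetitions, List B recall and delayed-recognition hits and false alarms, and to PILT accuracy and monetary amounts. The same paragraph uses t tests to follow up significant group-by-condition interactions, without Bonferroni correction.

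Three statements bear on the analysed group sizes:

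- Determination of Sample Size plans balance: "We will recruit 50 participants to the study (25 on PF-0499574 and 25 on placebo").
- The same section provides for replacement: "Participants who withdraw during the study or do not provide complete data-sets will be replaced".
- Data Cleaning says "Outliers will be excluded on a per task basis". The sample-size section expects such losses, since "to account for the exclusion of low quality data before analysis, we will aim for 25 individuals with complete datasets per group".

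**The concern.** The choice between the pooled and the unequal-variance test depends on a preliminary test of the same data. At this sample size a non-significant Levene's test is weak evidence that the variances are equal. When it fails to reject, the pooled standard error is used. That is harmless in equal groups but biased in unequal groups whose variances differ. Because exclusions are made separately for each task, group sizes may differ from task to task.

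At stake is the nominal 5% level of the t tests listed above. Some of them belong to the AVLT, which is named in the primary aim, and the post hoc tests follow up interactions such as those in the seven-emotion FERT ANOVA.

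**Working it through.** **Inputs from the SAP.** 25 per group planned; false positive rate 0.05; correction conditional on Levene's test; exclusions per task. The SAP gives no error rate for this rule, so there is no figure of its own to reproduce. Its 19 per group comes without an effect size and plays no part here.

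**Assumed inputs.** Analysed sizes from 25:25 down to 18:25; SD ratios from 1 to 2; Levene's test at 5%, centred on the mean and, as a check, on the median; normal data, with a skewed case added.

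**Why imbalance matters.** The variance of the difference in means is σ₁²/n₁ + σ₂²/n₂. The pooled test estimates it, on average, by [((n₁−1)σ₁² + (n₂−1)σ₂²)/(n₁+n₂−2)] × (1/n₁ + 1/n₂). With σ₁ = 1.5 and σ₂ = 1:

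- 25:25: true 3.25/25 = 0.130; pooled 1.625 × 0.08 = 0.130. No bias.
- n₁ = 20, n₂ = 25: true 0.1125 + 0.04 = 0.1525; pooled (42.75 + 24)/43 × 0.09 = 0.1397. The ratio is 0.916, so the standard error is about 4% too small.
- n₁ = 25, n₂ = 20: true 0.09 + 0.05 = 0.14; pooled (54 + 19)/43 × 0.09 = 0.1528. The ratio is 1.091, so the standard error is about 4% too large.

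The direction of the error depends on which group is smaller.

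**Simulation under the null.** Normal data, two-sided 5%, mean-centred Levene, 100,000 runs per row (200,000 for 25:18). The simulation standard error at 100,000 runs is √(0.05 × 0.95/100,000) = 0.07 percentage points. The more variable group is listed first.

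| Sizes | SD ratio | Levene significant | Always pooled | SAP rule | Always Welch |
|---|---|---|---|---|---|
| 25:25 | 1.5 | 43% | 4.8% | 4.8% | 4.8% |
| 22:25 | 1.5 | 41% | 5.6% | 5.3% | 5.0% |
| 20:25 | 1.5 | 40% | 6.2% | 5.65% | 5.1% |
| 18:25 | 1.5 | 38% | 6.8% | 5.9% | 5.1% |
| 25:20 | 1.5 | 38% | 4.2% | 4.6% | 5.0% |
| 25:18 | 1.5 | not tabulated | 3.7% | 4.3% | 4.9% |
| 25:25 | 2 | 85% | 5.2% | 5.0% | 5.0% |
| 20:25 | 2 | 81% | 6.9% | 5.2% | 4.9% |
| 18:25 | 2 | 79% | 7.9% | 5.6% | 5.1% |
| 25:20 | 2 | 80% | 3.8% | 4.8% | 5.0% |

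A further set of 100,000 runs gave 5.5% at 20:25 and 5.9% at 18:25 for the SAP rule at ratio 1.5, hence the range 5.5-5.9%. Median centring detects less: 38% at 25:25 and ratio 1.5, and 82% (25:25) and 77% (20:25) at ratio 2. It gives 5.7% and 6.0% error at 20:25 and 18:25 for ratio 1.5.

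**Skewed data** (gamma, shape 2, 20:25, SD ratio 1.5 to 2): SAP rule 5.5-6.4%, Welch 5.4-5.8%.

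**Power cost of Welch with equal variances**, standardised difference 0.8: 79.2% v 79.3% at 25:25, and 73.8% v 74.0% at 20:25. A further run put the loss at no more than about 0.3 points.

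**The case against.** The case against is substantial. The rule is prespecified and conventional, and it contradicts nothing else in the SAP. The design aims for 25 complete datasets per group and replaces incomplete participants. Reaching 18 v 25 means losing 7/25 = 28% of one arm and none of the other. Cleaning is done before unblinding, so knowledge of allocation should not drive exclusions. The AVLT is a pen-and-paper task, to which the response-time cut-offs have no obvious application. Inflation also needs the smaller group to be the more variable one. Averaged over both directions the error is close to nominal: (5.9 + 4.3)/2 = 5.1% at 18:25.

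Most of this stands, and it limits the size of the point. Two parts are weaker than they look. The version record describes data collection as complete, so exclusions made at cleaning after that date could not be made good by replacement. Blinded cleaning prevents deliberate imbalance but does not equalise the numbers removed.

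The objection about data type also stands in part. Intrusions, repetitions and false alarms are counts and may be skewed. In the skewed case Welch does not return exactly to 5%, although it stays closer to it than the stated rule.

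A reader might infer that Levene's test usually misses whatever variance difference exists. That holds up to a ratio of about 1.5. Large differences are usually caught, which is why the SAP rule at 18:25 does no worse at ratio 2 than at 1.5.

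**Conclusion.** The point holds as a minor improvement. Making the correction depend on Levene's test brings no benefit. Where groups are unequal and variances differ moderately, it moves the two-sided error from 5% to about 5.5-5.9%, or to about 4.3-4.6% in the opposite configuration, while Welch stays at about 5% for normal data. At 25 v 25 the rule is accurate.

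These figures rest on assumed group sizes and SD ratios that the SAP neither supplies nor rules out.

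Two stronger readings are not supported. One is that per-task exclusions make the t tests invalid. Under the SAP's rule the error stays at or below about 6% down to 18:25 with normal data; the 6.8% and 7.9% above belong to a pooled test with no check, which the SAP does not propose. The other is that the primary analyses are compromised. List A immediate and delayed recall and the FERT outcomes are analysed by ANOVA, which this rule does not govern. Only the other AVLT counts, PILT accuracy and amounts, and the post hoc t tests are affected.

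**What to change.** Replace the sentence on Levene's test with one stating that all independent-samples t tests, including post hoc tests, use Welch's unequal-variance t test whatever the result of any variance test. This removes a data-dependent step and two unstated choices (the level and the centring of Levene's test). Welch is already the default of t.test in R, the SAP's stated software. The cost is one sentence, no extra analysis work, and at most about 0.3 points of power when variances are equal. If the t tests have already been run, reporting the Welch results alongside them would show whether any conclusion depends on the choice.
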